6.1.4.3 Evaluation of Best Objective Response

The best objective response is the best response recorded from the start of the treatment until disease progression/recurrence (taking as reference for progressive disease the smallest measurements recorded since the treatment started). The subject’s best response assignment will depend on the achievement of both measurement and confirmation criteria.

Time point response: patients with target (+/- non-target) disease.			
Target lesions	Non-target lesions	New lesions	Objective response
CR	CR	No	CR
CR	Non-CR/non-PD	No	PR
CR	Not evaluated	No	PR
PR	Non-PD or not all evaluated	No	PR
SD	Non-PD or not all evaluated	No	SD
Not all evaluated	Non-PD	No	NE
PD	Any	Yes or No	PD
Any	PD	Yes or No	PD
Any	Any	Yes	PD

CR = complete response, NE = not evaluable, PD = progressive disease, PR = partial response, SD = stable disease.

Time point response: patients with non-target disease only.		
Non-target lesions	New lesions	Objective response
CR	No	CR
Non-CR/non-PD	No	Non-CR/non-PD
Not all evaluated	No	NE
Unequivocal PD	Yes or No	PD
Any	Yes	PD

CR = complete response, NE = not evaluable, PD = progressive disease

6.1.5 Duration of Response

Duration of objective response: The duration of objective response is measured from the time measurement criteria are met for CR or PR (whichever is first recorded) until the first date that recurrent or progressive disease is objectively documented (taking as reference for progressive disease the smallest measurements recorded since the treatment started).

The duration of overall CR is measured from the time measurement criteria are first met for CR until the first date that recurrent disease is objectively documented.

Duration of stable disease: Stable disease is measured from the start of the treatment until the criteria for progression are met, taking as reference the smallest measurements recorded since the treatment started.

6.1.6 Progression-Free Survival

Progression-free survival (PFS) is defined as the duration of time from start of treatment to time of progression.

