2.2 Secondary Objectives

2.2.1 To determine the disease control rate, overall survival, 6-month progression-free survival, and duration of response of combination axitinib, bavituximab, and avelumab compared to historical controls.

2.2.2 To evaluate the overall safety profile of combination axitinib, bavituximab, and avelumab.

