2.4 Endpoints

Primary endpoint:

Objective response rate (ORR) based on Investigator assessment per RECIST v.1.1.

Secondary endpoint:

Progression-free survival (PFS), overall survival (OS), and duration of response (DR) based on Investigator assessment, per RECIST v.1.1.

Adverse events (AEs) and laboratory abnormalities as graded by National Cancer Institute (NCI) Common Terminology Criteria for Adverse Events (CTCAE) v5.0.

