4.5 Duration of Therapy

Study treatment with axitinib, avelumab, and bavituximab will continue until disease progression, unacceptable toxicity, death, or discontinuation from the study treatment for any other reason.

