10.3 Data Analyses

Objective response rate, and disease control rate with corresponding 2-sided 95% CIs will be estimated using the Clopper-Pearson method. Kaplan-Meier methods will be used to estimate medians and 95% CIs for duration of response, overall survival, and progression-free survival. Survival outcomes will be calculated from Day 1 of Cycle 1. Descriptive statistics will be used to analyze AEs described according to the NCI CTCAE v5.0. Clinically significant laboratory abnormalities will be described as well. Serious adverse events will be summarized, including a causality assessment. The number of treatment cycles and doses administered will be summarized using descriptive statistics.

Associations between molecular features and tumor response will be analyzed using the Fisher-exact test with Benjamini-Hochberg multiple-testing correction. Cox regression models will be used to assess for associations between overall survival or progression-free survival and exploratory and correlative measures.

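### PFS and duration of response do not count death as an event, so followed literally "PFS" is time to progression

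*Combined protocol and SAP*

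**What the plan says.** Section 6.1.6 is the only place where PFS is defined: "Progression-free survival (PFS) is defined as the duration of time from start of treatment to time of progression". Section 6.1.5 measures duration of response "until the first date that recurrent or progressive disease is objectively documented", and duration of complete response ends at documented recurrence alone.

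Section 2.4 lists the secondary endpoints "Progression-free survival (PFS), overall survival (OS), and duration of response (DR) based on Investigator assessment", with RECIST v1.1 as the standard, but gives no event list. Section 2.2 sets as an objective "6-month progression-free survival, and duration of response of combination axitinib, bavituximab, and avelumab compared to historical controls".

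Section 10.3 states that "Kaplan-Meier methods will be used to estimate medians and 95% CIs for duration of response, overall survival, and progression-free survival" and that "Cox regression models will be used to assess for associations between overall survival or progression-free survival and exploratory and correlative measures". It fixes the time origin ("Survival outcomes will be calculated from Day 1 of Cycle 1") but names neither the events nor the censoring rules.

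Death appears elsewhere, but not as an event for these outcomes. Section 4.5 (Duration of Therapy) says treatment "will continue until disease progression, unacceptable toxicity, death, or discontinuation from the study treatment for any other reason". Section 4.6 follows survival about every 3 months for up to 2 years.

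**The concern.** PFS is ordinarily time to progression or death, whichever comes first. With death left out, what remains is time to progression, a different endpoint. The protocol's own background treats that as a separate endpoint when it describes the earlier single-arm trial of bavituximab plus sorafenib (Section 1.2.9).

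The literal definition implies that a patient who dies without documented progression is censored, as if still at risk of progressing later. Such deaths are unfavourable outcomes, so every one that is censored makes PFS, 6-month PFS and duration of response look better. Section 4.5 lists death separately from progression as a reason treatment ends, so the plan itself allows for such deaths.

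What is at stake is interpretation. If the historical controls count death, the comparison in Section 2.2 is not like-for-like, and the mismatch favours the new regimen.

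**Working it through.** **1. Text check.** The point rests on the definitions, so each relevant section was read for an event list.

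| Section | Content on PFS or duration of response | Death an event? |
|---|---|---|
| 2.2, 2.4 | Outcomes named; investigator assessment by RECIST v1.1 | Not stated |
| 4.5 (Duration of Therapy) | Death ends treatment | Not linked to PFS |
| 4.6 | Death ends survival follow-up | Not linked to PFS |
| 6.1.4 | Response and progression criteria | No |
| 6.1.5 | Ends at recurrence or progression | No |
| 6.1.6 | Ends at progression | No |
| 10.3 | Method and time origin | Not stated |

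**2. The plan's own figures.** There is no PFS or duration-of-response assumption to reproduce. The only design figures are for response rate (Section 10.2). An exact two-stage binomial calculation (14 then 29 patients, continue at 2 or more responses, reject at 7 or more) gives type I error 0.0973 at 14% and power 0.9002 at 34%. This agrees with the stated 0.10 and 0.9, and nothing here changes it.

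**3. Size of the effect on PFS.** Let *d* be the share of first events that are deaths without documented progression. The documents do not give it; 0% to 20% is assumed. Under constant hazards with true median *m*, the total hazard is λ = ln 2 / *m*. Censoring those deaths leaves a hazard of λ(1 − *d*), so:

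- apparent median = *m* / (1 − *d*)
- apparent 6-month PFS = exp(−6λ(1 − *d*)), which for *m* = 6 is 0.5^(1 − *d*)

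| *d* | Median multiplied by | Median if true value is 6.0 | 6-month PFS if true value is 50.0% |
|---|---|---|---|
| 0% | 1.000 | 6.0 | 50.0% |
| 5% | 1.053 | 6.3 | 51.8% |
| 10% | 1.111 | 6.7 | 53.6% |
| 20% | 1.250 | 7.5 | 57.4% |

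At *d* = 20%, other assumed medians give similar shifts: 35.4% becomes 43.5% for *m* = 4, and 59.5% becomes 66.0% for *m* = 8.

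**4. With the scan schedule included.** A simulation used 29 patients, 3,000 runs per value of *d*, an assumed 6.0-month median, progression read at the next 8-weekly scan (Section 5.3, footnote e) and administrative censoring at 24 to 48 months. The mean 6-month Kaplan-Meier estimates, death counted versus not counted, were:

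- *d* = 0%: 0.526 versus 0.526
- *d* = 5%: 0.529 versus 0.548
- *d* = 10%: 0.523 versus 0.562
- *d* = 20%: 0.525 versus 0.601

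The rises are about 0, 2, 4 and 8 points. Censoring at the death date or at the last scan made no difference.

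**5. Against sampling error.** At 50% with 29 patients the standard error is √(0.5 × 0.5 / 29) = 0.093, giving a 95% interval of about 31.8% to 68.2%. For an exponential median of 6.0 months with 29 events, the exact 95% interval is 4.3 to 9.0 months. The shifts in steps 3 and 4 are smaller than these margins.

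**6. Duration of response.** Suppose there are 7 responders (the rejection boundary in Section 10.2), all have an event, and one of those events is such a death. The exponential estimate is then multiplied by 7/6 = 1.17, against a 95% interval of 0.54 to 2.49 times the estimate. For one among 10 the factor is 10/9 = 1.11, against 0.59 to 2.09.

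**The case against.** The strongest reply is that this is an omission and not a choice. The endpoint has survival in its name, Section 10.3 groups it with survival outcomes, and an analyst might well count deaths anyway. It is true that the documents never say such deaths are censored; that is only what the literal definition implies. But the protocol chose to define the term, and an analyst who followed Section 6.1.6 would be following the plan. Citing RECIST v1.1 does not close the gap, because no text imports a PFS event list from it.

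Second, *d* may be small. Treatment runs until progression, remaining drugs may continue when one is stopped (Section 4.2.3), scans are 8-weekly, and there is an end-of-treatment scan. Section 5.4 also recognises clinical progression, which could precede some cancer deaths, although Section 2.4 ties the endpoint to RECIST v1.1. Against this, the Section 5.3 table schedules no tumor measurements after the end-of-treatment visit. A patient who stops all drugs for toxicity has no further protocol scan, so death may be the only later event recorded.

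Third, the size is assumed, and no control value, control definition or decision rule is stated for these outcomes. That stands. It limits the harm to interpretation, but it does not make the definition right.

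Finally, simply adding death leaves open how to treat a death long after the last scan. That also stands, and the fix below covers it.

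**Conclusion.** The definitions are wrong as written. Sections 6.1.5 and 6.1.6 leave death out, and no other section supplies it. If such deaths are censored, the reported PFS, 6-month PFS and duration of response are overstated relative to a death-inclusive definition whenever one occurs.

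The size rests on an assumed *d*, constant hazards and, for the 6-month figures, an assumed median. It runs from nothing at *d* = 0% to a 25% longer median at *d* = 20%. That is within the noise of a 29-patient trial, but the bias always favours the regimen and the confidence intervals do not reflect it.

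No go/no-go decision depends on these outcomes. This should be fixed, but it does not threaten the trial's main result.

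**What to change.** - **Section 6.1.6:** define PFS as time from Cycle 1 Day 1 to first RECIST v1.1 progression or death from any cause, whichever comes first.
- **Section 6.1.5:** end duration of response at progression or death from any cause. Treat duration of complete response in the same way, with recurrence or death.
- **Section 10.3:** censor patients without an event at the last adequate tumor assessment. State in advance how a death after a long gap without scans, or after new anticancer therapy, is handled.
- If time to progression is wanted, report it under that name as a separate endpoint.

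The cost is a few sentences in an amendment, which Section 11.6 requires the IRB to approve before use. The event definition needs no new data, because Section 4.6 already collects survival. PFS and duration of response will look slightly less favourable if such deaths occur. Making the change before results are known avoids a post hoc choice of definition.

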6.2 Safety/Tolerability

Analyses will be performed for all subjects having received at least one dose of study therapy. The study will use the CTCAE version 5.0 for reporting of adverse events. https://ctep.cancer.gov/protocolDevelopment/electronic_applications/ctc.htm

A safety lead-in phase composed of the first six patients evaluable for dose-limiting toxicities as defined in Section 4.2 will be performed to ensure the safety and tolerability of this triplet regimen.

7.0 ADVERSE EVENTS

7.1 Axitinib

For the most recent safety update, please refer to the current axitinib investigator's brochure.

7.1.1 Contraindications

None

7.1.2 Special Warnings and Precautions for Use

Aneurysms and artery dissections

VEGF pathway inhibitors may promote the formation of aneurysms and/or artery dissections. Before initiating axitinib, this risk should be carefully considered in patients with risk factors such as hypertension or history of aneurysm.

Elevation of Hemoglobin or Hematocrit

Increases in hemoglobin or hematocrit, reflective of increases in red blood cell mass, may occur during treatment with axitinib. An increase in red blood cell mass may increase the risk of thromboembolic events.

Hemoglobin or hematocrit should be monitored before initiation of, and periodically throughout, treatment with axitinib. If hemoglobin or hematocrit becomes elevated above the normal level, patients should be treated according to standard medical practice to decrease hemoglobin or hematocrit to an acceptable level.

Gastrointestinal Perforation and Fistula Formation

In pooled clinical studies with axitinib for the treatment of patients with renal cell carcinoma, gastrointestinal perforation and fistula were reported in 13/672 patients (2%) receiving axitinib. Monitor for symptoms of gastrointestinal perforation periodically throughout treatment with axitinib.

Wound Healing Complications

In the Phase 3 study A4061032 with axitinib for the treatment of patients with renal cell carcinoma, all-causality adverse events suggestive of wound healing complications were reported in 4/359 patients (1%). Treatment with axitinib should be stopped at least 24 hours prior to scheduled surgery. The decision to resume axitinib therapy after surgery should be based on clinical judgment of adequate wound healing.

Reversible Posterior Leukoencephalopathy Syndrome

In pooled clinical studies with axitinib for the treatment of patients with renal cell carcinoma, reversible posterior leukoencephalopathy syndrome was reported in 2/672 patients (<1%) receiving axitinib. In patients with signs/symptoms of reversible posterior leukoencephalopathy syndrome, axitinib should be permanently discontinued.

Heart failure events

In a controlled clinical study with axitinib for the treatment of patients with Renal Cell Carcinoma (RCC), heart failure events were reported in 1.7% of patients receiving axitinib. Grade 3/4 and 5 cardiac failure events were observed in 0.6% and 0.6% of patients receiving axitinib, respectively. Monitor for signs or symptoms of cardiac failure periodically throughout treatment with axitinib.

Hypertension

In pooled clinical studies with axitinib for the treatment of patients with renal cell carcinoma, hypertension was reported in 51% of patients receiving axitinib. Grade 3 and 4 hypertension was reported in 22% and 1% of patients receiving axitinib, respectively.

Blood pressure should be well-controlled prior to initiating axitinib. Patients should be monitored for hypertension and treated as needed with standard anti-hypertensive therapy. For persistent hypertension despite use of anti-hypertensive medications, axitinib dose should be reduced. For severe hypertension, axitinib should be held and resumed at a lower dose level once

hypertension is improved. If axitinib is interrupted, patients receiving antihypertensive medications should be monitored for hypotension.

Thyroid dysfunction

In clinical studies with axitinib for the treatment of patients with Renal Cell Carcinoma (RCC), hypothyroidism was reported in 25% of patients receiving axitinib. Hyperthyroidism was reported in 2% of patients receiving axitinib. Monitor thyroid function before initiation of, and periodically throughout treatment with axitinib. Hypothyroidism and hyperthyroidism should be treated according to standard medical practice to maintain euthyroid state.

Arterial thromboembolic events

In clinical studies with axitinib for the treatment of patients with Renal Cell Carcinoma (RCC), arterial thromboembolic events were reported in 3% of patients receiving axitinib. Grade 3 events were reported in 1% and Grade 4 events were reported in 1% of patients.

Axitinib should be used with caution in patients who are at risk for, or who have a history of these events.

Venous thromboembolic events

In clinical studies with axitinib for the treatment of patients with Renal Cell Carcinoma (RCC), venous thromboembolic events were reported in 3% of patients receiving axitinib. Grade 3 and 4 venous thromboembolic events were reported in 2% of patients.

Axitinib should be used with caution in patients who are at risk for, or who have a history of these events.

Hemorrhage

In clinical studies with axitinib for the treatment of patients with Renal Cell Carcinoma (RCC), hemorrhagic events were reported in 26% of patients receiving axitinib. Grade 3 and 4 hemorrhagic events were reported in 3% and 1% of patients. If any bleeding requires medical intervention, temporarily interrupt the axitinib dose.

Proteinuria

In clinical studies with axitinib for the treatment of patients with Renal Cell Carcinoma (RCC), proteinuria was reported in 21% of patients receiving axitinib. Grade 3 and 4 proteinuria were reported in 5% and <1% of patients receiving axitinib, respectively. Monitoring for proteinuria before initiation of, and periodically throughout, treatment with axitinib is recommended. For patients who develop moderate to severe proteinuria, reduce the dose or temporarily interrupt axitinib treatment.

Hepatic impairment

A dose decrease is recommended when administering axitinib to patients with moderate hepatic impairment (Child-Pugh class B). Axitinib has not been studied in patients with severe hepatic impairment (Child-Pugh class C). Monitor ALT, AST and bilirubin before initiation of and periodically throughout treatment with axitinib.

7.1.3 Interaction with other medications

Axitinib is metabolized primarily by CYP3A4/5 and, to a lesser extent, CYP1A2, CYP2C19, and uridine diphosphate-glucuronosyltransferase (UGT) 1A1. Inhibitors of CYP3A4/5 such as ketoconazole, itraconazole, clarithromycin, atazanavir, indinavir, nefazodone, nelfinavir, ritonavir, saquinavir, and telithromycin may

increase axitinib plasma concentrations. Grapefruit may also increase axitinib plasma concentrations. Selection of concomitant medication with no or minimal CYP3A4/5 inhibition potential is recommended. If a strong CYP3A4/5 inhibitor must be co-administered, a dose decrease of axitinib by approximately half is recommended.

Strong inducers of CYP3A4/5 including rifampin, dexamethasone, phenytoin, carbamazepine, rifabutin, rifapentine, phenobarbital, and Hypericum perforatum (St. John's wort) may decrease axitinib plasma concentrations. Selection of concomitant medication with no or minimal CYP3A4/5 induction potential is recommended. If a strong CYP3A4/5 inducer must be co-administered, a dose adjustment of axitinib is recommended.

7.1.4 Adverse Reactions

The following side effects are suspected to be related to axitinib treatment for reporting purposes:

- Cardiac failure events (cardiac failure, cardiopulmonary failure, left ventricular dysfunction, and right ventricular failure)
- Palmar-plantar erythrodysesthesia
- Hypertension
- Aneurysms and artery dissections
- Thyroid dysfunction
- Arterial thromboembolic events
- Venous thromboembolic events
- Increased Hemoglobin/hematocrit
- Hemorrhage
- Gastrointestinal perforation
- Wound healing complications
- Posterior reversible encephalopathy syndrome
- Proteinuria
- Diarrhea
- Increased serum creatinine

7.2 Avelumab

7.2.1 Contraindications

None

7.2.2 Special Warnings and Precautions for Use

Infusion related reactions

Avelumab can cause severe or life-threatening infusion reactions. Patients should be premedicated with antihistamine and acetaminophen prior to infusions. Monitor patients for signs and symptoms including pyrexia, chills, flushing, hypotension, dyspnea, wheezing, back pain, abdominal pain, and urticaria. Interrupt or slow the rate of infusion for mild or moderate Infusion-Related Reactions (IRRs). Stop the infusion and permanently discontinue avelumab for severe (Grade 3) or life-threatening (Grade 4) infusion reactions.

Immune related AEs (irAEs)

Avelumab treatment may result in severe and rarely fatal immune-related toxicities. irAEs may affect any organ causing pneumonitis, hepatitis, colitis, dermatitis/rash, endocrinopathies, myalgias/artralgias, or nephritis. Less

frequent irAEs include myositis, myocarditis, hypophysitis, uveitis, myasthenia gravis, and Guillan-Barre syndrome. For suspected immune-related adverse reactions, evaluation should include investigations to rule out non-immune causes of symptoms. Depending upon the severity of the adverse reaction, Avelumab may be delayed or permanently discontinued. Depending on the type of irAE, management may include hormone supplementation, corticosteroids, non-steroid immunosuppressants, or biologic agents.

7.2.3 Interaction with other medications

No interaction studies have been conducted with avelumab in humans.

7.2.4 Adverse Reactions

The following side effects are suspected to be related to avelumab treatment for reporting purposes:

- Infusion reaction
- Hypothyroidism
- Adrenal insufficiency
- Hyperthyroidism
- Hypothyroidism
- Hypopituitarism
- Uveitis
- Colitis
- Autoimmune hepatitis
- Pancreatitis
- Type 1 diabetes mellitus
- Myositis
- Guillan-Barre syndrome
- Nephritis
- Pneumonitis
- Rash/dermatitis

7.3 Baviximab

7.3.1 Contraindications

Known allergy or hypersensitivity to any component of the drug product or prior Grade ≥ 3 infusion reaction, hypersensitivity, or anaphylaxis after receiving any other monoclonal antibody therapy.

7.3.2 Special Warnings and Precautions for Use

Infusion related reactions

Bavituximab can cause infusion reactions. Monitor patients for signs and symptoms including pyrexia, chills, flushing, hypotension, dyspnea, wheezing, back pain, abdominal pain, and urticaria. Interrupt or slow the rate of infusion for mild or moderate IRRs. Stop the infusion and permanently discontinue bavituximab for severe (Grade 3) or life-threatening (Grade 4) infusion reactions.

